9.4. Variables

Table 1. Study variables and operational definitions

Main Study

Index date-1= start date of alectinib treatment during the study identification period

Index date-2= start date of the subsequent treatment following alectinib, among patients who receive a next treatment during the study identification period

Exploratory Analysis

Index date-1= start date of lorlatinib treatment during the study identification period

Index date-2= start date of the subsequent treatment following lorlatinib, among patients who receive a next treatment during the study observation period

Table 1. Study variables and operational definitions

Variable	Source(s)	Role(s) in study	Period of measurement	Operational definition
Demographic at	nd patient ch	aracteristics		
PatID	iKM structured data	Data linkage	Study observation period	Unique patient identifier that will be used to link clinical records. This information will not be disclosed to the study sponsor.
Medical record number (MRN)	iKM structured data	Data linkage	Study observation period	Unique patient identifier that will be used to link clinical records. This information will not be disclosed to the study sponsor.
Clinical trial participation	iKM structured data + chart review	Eligibility criteria	Follow-up	Patients enrolled in interventional clinical trials (patients in only observational studies will be retained, if applicable) in The US Oncology Network or Non-Network during the study observation period will be flagged.
Other cancer diagnosis	iKM structured data + chart review	Eligibility criteria	Prior medical history + study observation period	Patients will be confirmed as having no additional primary or secondary malignancies (with the exception of non-melanotic skin cancer) within the 5 years prior to and after the index date-1. Patients with a secondary diagnosis or receipt of treatment indicated for another primary cancer within 5 years prior to index date-1 will be excluded.
Additional visits	iKM structured data	Eligibility criteria	Follow-up	To capture a sample of patients with longitudinal records, patients will be required to have 2 records of either additional visits following the index date-1 visit and/or a record of death prior to the end of the study follow-up period. Visits are defined as physical encounters with the practice, detected by vital sign records. There will be no distinction made, for purposes of inclusion, between patients that have an

Table 1. Study variables and operational definitions

Variable	Source(s)	Role(s) in study	Period of measurement	Operational definition
				additional US Oncology Network or Non- Network visit and those with a record of death. There is no minimum or maximum requirement on time from index date-1 to these qualifying events.
Gender	iKM structured data + chart review	Baseline characteristic	Prior medical history	Patients will be categorized as: Male Female
Date of birth	iKM structured data	Eligibility; Data linkage; Baseline characteristic	Prior medical history	Patient's date of birth as recorded in iKM. This information will not be disclosed to the study sponsor.
Age	iKM structured data (derived)	Eligibility; Baseline characteristic	Baseline	Patient's age (in years) at the date of diagnosis, which will be calculated as the integer of [(diagnosis date – date of birth + 1) / 365.25]. Patients aged less than 18 years at the initial recorded diagnosis of NSCLC will be excluded from the study.
Age groups	iKM structured data (derived)	Baseline characteristic	Baseline	Multiple age categories will be created based on the continuous age data: <65 years ≥65 years No information
Race	iKM structured data	Baseline characteristic	Prior medical history	Categorized as: Caucasian African American Asian Native American Other No information The specific categories outside of Caucasian and African American will be confirmed after reviewing sample sizes and the added value to the study with Ontada's Privacy and Compliance team.
Smoking history	iKM structured data	Baseline characteristic	Baseline	Categorized as: Never smoked Current smoker Former smoker No information
Healthcare set	ting and provi	der characterist	ics	
Practice location	iKM structured data (derived)	Baseline characteristic	Baseline	The US census region of The US Oncology Network clinic where the patient received care at the index visit: Midwest: Illinois, Indiana, Michigan, Ohio, Wisconsin, Iowa, Kansas, Minnesota,

Table 1. Study variables and operational definitions

Variable	Source(s)	Role(s) in study	Period of measurement	Operational definition
				Missouri, Nebraska, North Dakota and South Dakota Northeast: Connecticut, Maine, Massachusetts, New Hampshire, Rhode Island, Vermont, Pennsylvania, New Jersey and New York South: Delaware, Florida, Georgia, Maryland, North Carolina, South Carolina, Virginia, Washington D.C., West Virginia, Alabama, Kentucky, Mississippi, Tennessee, Arkansas, Louisiana, Oklahoma and Texas West: Arizona, Colorado, Idaho, Montana, Nevada, New Mexico, Utah, Wyoming, California, Oregon and Washington State Missing clinic values will be captured in a "no information" category. Some of the regions may need to be collapsed if there are small sample sizes (e.g., South vs. non- South). This determination will be confirmed after reviewing sample sizes and the added value to the study with Ontada's Privacy and Compliance team.
Disease charact				
Initial NSCLC diagnosis	iKM structured data + chart review	Eligibility criteria, Baseline characteristic	Medical history prior to index	To assess NSCLC diagnoses that occurred prior to index date-1, patients' available medical history in iKM will be searched. The completeness of this history will vary based on the length of disease and the time within The US Oncology Network or Non-Network. Records may also be incomplete for patients with an initial NSCLC diagnosis that occurred outside of The US Oncology Network or Non-Network. Diagnosis of NSCLC will be determined through a review of iKM's discrete diagnosis and histology fields, which are populated during the routine course of care (International Classification of Diseases [ICD] codes will not be used). If no initial diagnosis date is documented, the first recorded diagnosis date in iKM will be used. This date will be used in calculations, not reported separately. Patients without a recorded diagnosis of NSCLC will be excluded from the study.
Stage at initial NSCLC diagnosis	iKM structured data	Baseline characteristic	Medical history prior to index	Categorized as: Early stage (IA, IB, IIA, IIIB) Limited/Regional (IIIA) Locally advanced (IIIB)

Table 1. Study variables and operational definitions

Variable	Source(s)	Role(s) in study	Period of measurement	Operational definition
		•		Metastatic (IV) Unknown
Date of metastatic disease diagnosis	iKM structured data + chart review	Baseline characteristic	Medical history prior to index	Date of first recorded diagnosis of metastatic disease within the EHR. Patients will be qualified initially based on the date identified in the structured data; this will be confirmed during chart review among patients selected for chart review. Ultimately, the primary source will be the chart if available. All patients receiving ALK inhibitors are assumed to be metastatic at time of ALK inhibitor treatment. Structured data will confirm the patient as metastatic and as available, indicate the earliest associated date of any of these criteria: 1) Stage IV disease 2) TNM with M value of 1 3) Record of location of metastatic disease 4) Current or prior disease status containing reference to metastatic disease
Metastatic disease at diagnosis	iKM structured data + chart review	Categorized as: Baseline characteristic	At diagnosis	Categorized as: Yes No No information Note, "no information" can indicate that metastases were not documented in the chart, not necessarily that patients did not have metastases.
Distant metastatic site(s) at index date-1 (alectinib or lorlatinib start date)	iKM structured data + chart review	Baseline characteristic	Baseline	Baseline metastatic location(s) will be identified and categorized as: Bone (single) Bone (multiple) Brain CNS Liver (single) Liver (multiple) Lung (single) Lung (single) Lung (pleural effusion) Lymph nodes (regional) Lymph nodes (distant) Ovary Other No information Note, "no information" can indicate that metastases were not documented in the chart, not necessarily that patients did not have metastases.

Table 1. Study variables and operational definitions

Variable	Source(s)	Role(s) in study	Period of measurement	Operational definition
Tumor histology	iKM structured data	Baseline characteristic	Baseline	Categorized as: Adenocarcinoma Squamous Large Not otherwise specified (NOS) Missing/unknown
ALK testing order source and date	iKM Chart Review	Baseline characteristic	Baseline	Categorized as: Lab report Order requisition Pathology report Progress note
ALK mutation status	iKM structured data + Chart Review	Baseline characteristic	Baseline	Categorized as: Not performed Positive fusion/rearrangement Negative Equivocal Indeterminate QNS Other Inconclusive Not documented If multiple test results are available, used last documented value
Biopsy type for ALK testing	Chart Review	Baseline characteristic	Baseline	Categorized as: Pleural Tissue Blood Other Not documented
Assay type for ALK testing	Chart Review	Baseline characteristic	Baseline	Categorized as: Fluorescence in situ hybridization (FISH) Immunohistochemistry (IHC) Next-generation sequencing (NGS) Reverse transcriptase—polymerase chain reaction (RT-PCDR) Other Not documented
Date of ALK mutation result BRAF (v-raf murine sarcoma viral oncogene homolog B1) mutation status	Chart Review iKM structured data	Baseline characteristic Baseline characteristic	Baseline Baseline	Date as captured in chart review Categorized as: BRAF V600E (Mutated) Mutations Wild-type Unknown

Table 1. Study variables and operational definitions

Variable	Source(s)	Role(s) in study	Period of measurement	Operational def	finition	
EGFR (epidermal growth factor receptor) mutation status	iKM structured data	Baseline characteristic	Baseline	Categorized as: EGFR sensitizin EGFR non-sensi T790M (+) EGFR mutation Equivocal Not performed Unknown	tizing mutation (+)
PD-L1 expression	iKM structured data	Baseline characteristic	Baseline	Categorized as: >= 50% Express 1-49% Expression Negative Unknown		
ROS1	iKM structured data	Baseline characteristic	Baseline	Categorized as: Positive, Negative, Unknown		
MET (Mesenchymal- to-epithelial transition) exon 14 mutations	iKM structured data	Baseline characteristic	Baseline	Categorized as: Positive, Negative, Unknown		
Eastern Cooperative Oncology Group (ECOG) performance status	iKM structured data	Baseline characteristic	Baseline	of a patient's dis	on rmance status is l be converted to v outlined below. ECOG Performance	living activities es indicating res: a similar ECOG using [20] ECOG Performance
				Status 100	Status 0	Status Description Fully active
				80, 90	1	Restricted in physically strenuous activity
				60, 70	2	Ambulatory and capable of self-care

Table 1. Study variables and operational definitions

eteristics iKM	study		40, 50	3	but unable to work Capable only of limited self-care
iKM			,		of limited self-care
iKM			10, 20, 30	4	a
iKM					Completely disabled
iKM			0	5	Dead
data + chart	Eligibility criteria, Treatment characteristics	Study observation period	the study iden	ntification period	alectinib during the
			and patient when exporatory an study.	ho did not receivalysis will be ex	ve lorlatinib for the scluded from the
structured data + chart review	Treatment pattern	observation period	patients for N	SCLC treatment	t prior to the index
iKM structured data + chart review	Treatment pattern	Study observation period			
iKM structured data + chart review	Treatment pattern	Study observation period			nhibitor during the
iKM structured data + chart review	Treatment pattern	Study observation period	is possible that not document follow-up or i treatment date will be used, v not have a sto therapy, the st	at the patient's tred if the patient s still on-therapy, death date or ewhichever is ear p date and initiatart date of the so	reatment stop date is dies, is lost-to y. The final end of study date cliest. If patient does tes a subsequent ubsequent therapy
iKM structured data + chart review	Treatment pattern	Study observation period	Immediate ne lorlatinib) and post-alectinib during the stu	xt treatment post subsequent treator (or post-lorlating dy period.	st-alectinib (or post- atments received nib) treatment
	iKM structured data + chart review	data + chart review iKM Treatment pattern iKM Treatment pattern	data + chart chart chart chart review iKM structured data + chart review iKM Treatment pattern iKM Treatment pattern iKM Structured data + chart review iKM Treatment pattern iKM Structured data + chart review iKM Treatment pattern iKM Structured data + chart review iKM Treatment pattern iKM Structured data + chart review iKM Treatment pattern iKM Structured data + chart review iKM Structured data + chart review iKM Structured data + chart review iKM pattern iKM Structured data + chart review iKM period Study observation period iKM structured data + chart review iKM period	data + chart review iKM structured pattern study structured data + chart review iKM structured pattern study structured observation period is possible that not document follow-up or it reatment date will be used, will be used, will be consided attary pattern observation lordatinib) and post-alectinib during the sture review *Lorlatinib tree *Lorlatinib tree	data + chart chart chart chart chart chart chart chart chart review iKM Treatment structured data + chart review iKM Treatment pattern observation period iKM Structured data + chart review iKM Treatment pattern observation period iKM Structured data + chart review iKM Treatment pattern observation period iKM Structured data + chart review iKM Treatment pattern observation period iKM Structured data + chart review iKM Treatment pattern observation period iKM Structured data + chart review iKM Treatment pattern observation period iKM Structured data + chart review iKM IT reatment pattern observation period iKM Structured data + chart review iKM IT reatment pattern observation period iKM IT reatment pattern observation period iKM IT reatment pattern observation period pattern pattern post-alectinib or post-lorlatinib during the study period.

Table 1. Study variables and operational definitions

Variable	Source(s)	Role(s) in study	Period of measurement	Operational definition	
Subsequent treatments (post alectinib or post- lorlatinib) start and end date(s)	iKM structured data + chart review	Treatment pattern	Study observation period	Date of initiation and end date of immediate next treatment post-alectinib (or post-lorlatinib) and subsequent treatments received post-alectinib (or post-lorlatinib) treatment during the study period. *Lorlatinib treatment for the exploratory analysis will be sourced from structured data only	
Reason for ALK inhibitor (alectinib, and subsequent treatment) treatment discontinuation	Chart review	Treatment characteristics	Study observation period	Data for alectinib and subsequent treatment discontinuation reason will exclusively come from chart review. Reviewers will be asked to select reason(s) as explicitly documented in patients' charts. If available, reason patients discontinued treatment will be abstracted: Completion of therapy Provider-documented disease progression Death Insurance/cost-related Loss to follow-up Patient preference Toxicity Other No information Reviewers will specify other reasons; these will be reported if any represent >5% of patients.	
ALK inhibitor treatment sequencing	iKM structured data + chart review	Treatment pattern	Study observation period	ALK inhibitor treatment paths (e.g. initiate crizotinib followed by ceritinib, initiate crizotinib followed by alectinib, etc.)	
Front-line alectinib	iKM structured data + chart review	Treatment pattern	Study observation period	First treatment administration of alectinib not preceded by any other product for NSCLC therapy except up to 3 months of chemotherapy and immunotherapy preceding alectinib therapy initiation to classify patient as receiving 1L alectinib	
Clinical outcomes					
Last US Oncology Network visit date	iKM structured data + chart review	Clinical outcomes	Study observation period	Each patient's most recent visit date, prior to or on close of study observation period, in the structured data will be recorded. A visit is defined as a physician encounter with the practice where either treatment is given, or vital signs are recorded. For patients with a death date, this last visit date should occur prior to the death date.	

Table 1. Study variables and operational definitions

Variable	Source(s)	Role(s) in study	Period of measurement	Operational definition
				This will not be reported separately; it will be used in calculating the patient's available follow-up time as a descriptive measure. Available follow-up time = Integer (latest of last visit date or death date – index date +1).7
Death date	iKM structured data + limited access death master file (LADMF) + chart review	Clinical outcomes	Study observation period	Date of death will be captured from the LADMF as well as iKM. If dates conflict between the 2 sources, the LADMF date will be prioritized. If severe data discordance is observed (i.e., death is reported to occur prior to the index date), then the iKM death date will be used.
Vital status	iKM structured data + LADMF + chart review (derived)	Clinical outcomes	Study observation period	Patients without a date of death in either the LADMF or iKM will be assumed to be alive at the end of the study. Those with a date of death in either LADMF or iKM will be flagged as deceased.
ALK inhibitor (alectinib and stratified by subsequent treatment) duration of therapy (DOT)	iKM structured data + chart review (derived)	Treatment characteristics	Study observation period	An intent to treat approach will be used. DOT will be defined as duration of time (in months) between alectinib initiation and discontinuation, or the last administration date of alectinib, or start date of a subsequent ALK inhibitor, or evidence of new non-ALK inhibitor treatment (as a proxy for evidence of discontinuation) will be used as a stop date. There may be some patients who do not have evidence of discontinuation or who do not move on to a subsequent therapy.
				Descriptive statistics (mean, median) and K-M methodology will be calculated from initiation of alectinib, until evidence of discontinuation for any reason, including but not limited to a treatment stop date, a last alectinib administration date, evidence of new ALK inhibitor treatment or non-ALK inhibitor treatment, death or check-in in a hospice. Patients who do not have evidence of discontinuing, starting new therapy, or whose last prescription date is <30 days from the end of

Table 1. Study variables and operational definitions

Variable	Source(s)	Role(s) in	Period of	Operational definition
		study	measurement	
				the study period, will be censored at last visit date or end of study period.
Overall survival (OS) (alectinib and stratified by subsequent treatment)	iKM structured data + LADMF + chart review (derived)	Clinical outcomes	Study observation period	OS will be defined as the interval (in months) between alectinib start date and the date of death (any cause) as documented in the LADMF and the iKM EHR database. OS will be reported for overall alectinib and stratified by subsequent treatment. Patients who did not die within the study observation period will be censored on the study end date or the last visit date available in the dataset, whichever occurred first. OS will be analyzed using the Kaplan-Meier method with 95% CIs, and summary tables of the number of events and censored patients 3, 6, 12, 18, and 24 months.
Progression date after index date (physician- assessed)	Chart review	Clinical outcomes	Study observation period	Physician-assessed disease progression (and corresponding date of note) recorded from physician's progress notes in Chart Review.
Progression- free survival (alectinib, and subsequent treatment)	iKM structured data + LADMF + chart review (derived)	Clinical outcomes	Study observation period	The PFS will be measured from the initiation of alectinib to the date of progression or date of death due to any cause, censoring patients who are still alive at the end of the study observation period and did not progress at the last visit date. PFS will be reported for overall alectinib and stratified by subsequent treatment. The PFS will be estimated in weeks using the Kaplan-Meier method with 95% CIs, and summary tables of the number of events and censored patients at 3, 6, 12, 18, and 24 months.

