9.3. Setting

The study population will consist of patients with a diagnosis of NSCLC receiving alectinib within The US Oncology Network and Non-Network sites. The US Oncology Network includes approximately 1,400 affiliated physicians operating in over 480 sites of care across states and treats approximately 1.2 million US cancer patients annually. There are more than 2,650 active Non-Network supported oncology and non-oncology sites of care. [19]

Figure 1 and Figure 2 presents graphical depictions of the study time periods, which are as follows:

- Phase 1 and 2 study observation period: 01 June 2017 31 December 2019.
- Phase 1 and 2 study identification period: 01 June 2017 30 June 2019.
- Phase 3 study refresh observation period: 01 June 2017 31 August 2021.
- Phase 3 study refresh identification period: 01 June 2017 31 August 2020.
- Phase 3 exploratory analysis study observation period: 02 November 2018 31 August 2021.
- Phase 3 exploratory analysis study identification period: 02 November 2018 31 August 2020.
- Phase 1 and 2 index date-1: start date of alectinib treatment during the study identification period
- Phase 1 and 2 index date-2: start date of the subsequent treatment following alectinib, among patients who receive the next treatment during the study observation period
- Phase 3 study refresh index date-1: start date of alectinib treatment during the study identification period
- Phase 3 study refresh index date-2: start date of the subsequent treatment following alectinib, among patients who receive the next treatment during the study observation period
- Phase 3 exploratory analysis index date-1: start date of lorlatinib treatment during the study identification period
- Phase 3 exploratory analysis index date-2: start date of lorlatinib treatment among patients who receive next treatment during the study observation period
- Baseline: The baseline period or "at index" includes up to 30 days prior to and up to 30 days after index. If a patient has multiple baseline values for a particular demographic or clinical characteristic during this ± 30-day time frame, the one closest (in absolute value) prior to the index date will be used. If no values prior to index are available, then the one closest to the index date up to 30 days after will be used.

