- Prior medical history: Patients' available history in the iKnowMed (iKM) EHR will vary based on the length of disease and the time within The US Oncology Network. Disease characteristics such as time of NSCLC diagnosis and date of metastatic

disease will take into account patients' available medical history. The prior medical history period will end the day prior to the index date-1.

• Follow-up: Patients will be followed through the end of the study observation period, date of last visit or date of death, whichever occurs first. For analysis, patients will have a potential of at least 6 months of follow-up duration; however, patients will have variable follow-up time periods, depending on their index dates and last contact dates.

9.3.1. Phase 1 and 2 (original study) and Phase 3 (refresh study) population Inclusion criteria

Patients must meet all of the following inclusion criteria to be eligible for inclusion in the study:

- 1. Patients with a documented diagnosis of NSCLC.
- 2. Patients \geq 18 years of age at initial recorded diagnosis of NSCLC.
- 3. Patients who received treatment with alectinib within The US Oncology Network or Non-Network sites during the study identification period.
- 4. During the study observation period, patients observed with at least 2 visits⁴ after the index date-1.

Exclusion criteria

Patients meeting any of the following criteria will not be included in the study:

- 1. Receipt of treatment indicated for another primary cancer or diagnosis of another primary cancer (with the exception of non-melanotic skin cancer), within 5 years of index date-1 will be excluded.
- 2. Patients enrolled in clinical trials prior to receiving alectinib during the study ID period (index date-1), will be excluded.

⁴ Visits are defined as physical encounters with the practice, detected by vital sign records. The second and third visits must be observed after the index date-1 to demonstrate continuity of care. There is no required time span between the additional visits and the index date-1.

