9.3.2. Phase 3 exploratory analysis study population

Inclusion criteria

Patients must meet all of the following inclusion criteria to be eligible for inclusion in the study:

- 1. Patients with a documented diagnosis of NSCLC.
- 2. Patients \geq 18 years of age at initial recorded diagnosis of NSCLC.
- 3. Patients who received treatment with lorlatinib within The US Oncology Network or Non-Network practices during the study identification period.
- 4. During the study observation period, patients observed with at least 2 visits⁴ after the index date-1.

Exclusion criteria

Patients meeting any of the following criteria will not be included in the study:

- 1. Receipt of treatment indicated for another primary cancer or diagnosis of another primary cancer (with the exception of non-melanotic skin cancer), within 5 years of index date-1 will be excluded.
- 2. Patients enrolled in clinical trials prior to receiving lorlatinib during the study ID period (index date-1) will be excluded.

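### Table 1 measures clinical-trial enrolment over follow-up or the observation period, whereas exclusion 2 concerns enrolment before index date-1

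*Combined protocol and SAP*

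**What the plan says.** For the main study, Section 9.3.1 states: "Patients enrolled in clinical trials prior to receiving alectinib during the study ID period (index date-1), will be excluded". Section 9.3.2 repeats the rule for the exploratory analysis, anchored on the other drug: "Patients enrolled in clinical trials prior to receiving lorlatinib during the study ID period (index date-1) will be excluded". Both look backwards from index date-1.

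Table 1 in Section 9.4 has one row on this subject, clinical trial participation. Its role is eligibility criteria. Its period of measurement is follow-up, and its definition starts "Patients enrolled in interventional clinical trials (patients in only observational studies will be retained, if applicable" and ends "in The US Oncology Network or Non-Network during the study observation period will be flagged".

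Section 9.3 defines the time windows. On follow-up it says "Patients will be followed through the end of the study observation period, date of last visit or date of death, whichever occurs first". For the look-back it says "The prior medical history period will end the day prior to the index date-1". The observation period is a calendar interval that does not depend on the patient's index date, for example "Phase 3 study refresh observation period: 01 June 2017 31 August 2021".

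**The concern.** The row that should put exclusion 2 into operation does not cover the window that exclusion 2 names. There are two consequences. Patients whom the exclusion targets may go unidentified and stay in the analysis. And an event after index, joining a trial once alectinib has started, sets a variable whose stated role is eligibility.

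The second consequence is the more serious. Objectives 2, 4, 6, 9 and 10 describe what happens after alectinib: the next treatment, PFS and OS. If patients were dropped because they joined a trial after index, the population would be selected on the pathway under study. Such a patient must also have been alive at enrolment, so the removal would not be random with respect to survival.

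The wording of this row carries weight because Section 9.8 says that no separate statistical analysis plan will be written, and Section 9.8.2 refers the derivations to Table 1. The row also draws on chart review, and Sections 9.3.4.1 and 9.3.4.2 have eligibility verified during abstraction. Programmers and abstractors could therefore apply different rules.

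**Working it through.** The plan states no figure that depends on this row, so the check sets the passages side by side and works out what each reading covers.

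**1. The target.** Exclusion 2 targets trial enrolment before index date-1.

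**2. The row read by its period column.** Follow-up ends at the close of observation, last visit or death, and Section 9.3 makes its length depend on the index date. It is therefore post-index time. Pre-index enrolments covered: none. Post-index enrolments covered: all that are recorded.

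**3. The row read by its definition.** The observation period starts on a fixed date, so

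pre-index days covered = index date-1 − start of observation period.

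For a patient indexed on the first day this is 0. For a patient indexed on the last day of identification it is the maximum below (dates from Section 9.3; months use the 30.4375-day month of the DOT formula in Section 9.8.3).

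| Analysis | Observation starts | Last index date | Maximum pre-index days covered |
|---|---|---|---|
| Phases 1 and 2 | 01 June 2017 | 30 June 2019 | 759 (24.9 months) |
| Phase 3 refresh | 01 June 2017 | 31 August 2020 | 1187 (39.0 months) |
| Phase 3 exploratory | 02 November 2018 | 31 August 2020 | 668 (21.9 months) |

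Enrolments before the start date are missed for everyone. Post-index enrolments up to the end of observation are all covered.

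**4. What the two readings share.** Each misses some or all of the targeted enrolments, and each attaches the eligibility flag to post-index enrolment. They also differ from each other, so the row is not consistent with itself.

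**5. Comparison with neighbouring rows.** A pre-index window is available and is used for other eligibility variables in Table 1. Other cancer diagnosis is measured over prior medical history plus the observation period, and initial NSCLC diagnosis over history before index. The trial row uses no such window.

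**6. Whether flagged patients could be removed.** Two features point that way. The parenthesis in "Patients enrolled in interventional clinical trials (patients in only observational studies will be retained, if applicable" has a purpose only if those in interventional trials might not be retained. And the additional-visits row, with the same pairing of eligibility role and follow-up period, does select patients. Two features point the other way: the verb is to flag, and Section 9.8.3 ties inclusion to the criteria in Section 9.3.1, none of which mentions enrolment after index.

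**7. Size.** Section 9.6 gives no trial-participation rate, before or after index. It does show that the group after alectinib is small: 20–30% of 293 is 0.20 × 293 ≈ 59 to 0.30 × 293 ≈ 88 patients. About half of the 293 were not front-line, so many have earlier treatment during which a trial could have been joined. Neither fact yields a count of patients affected.

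**The case against.** The best defence is that Section 9.3.1 governs. Exclusion 2 stands there as its own criterion, Section 9.8.3 requires that patients meet none of the exclusions listed in that section, exclusions are counted by criterion, and Section 9.7 has the attrition reviewed before further data are collected. Where Table 1 intends removal it says so outright, as it does for other cancers, for age under 18 and for no recorded NSCLC diagnosis. The trial row only flags.

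Much of this stands. A reader might infer that the plan orders the removal of anyone who joins a trial after alectinib. The documents do not support that; they leave it open. A reader might also infer that no pre-index enrolment can be found and that exclusion 2 is not applied at all. That is too strong: under the definition text, enrolment between the start of observation and index is covered, and the criterion itself remains in force.

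The defence does not remove the contradiction. If Section 9.3.1 governs, the row still does not measure what that section requires, and nothing says what is done with a flagged patient.

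The difference between clinical trials in the exclusions and interventional trials in Table 1 is minor. The narrower term can fairly be read as the operational definition of the broader one, and aligning them is tidying.

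**Conclusion.** The Table 1 row contradicts exclusion 2 in Sections 9.3.1 and 9.3.2, and no other text reconciles them. As written, the row misses either all targeted enrolments (period column) or those before 01 June 2017, or 02 November 2018 for lorlatinib (definition). On both readings it sets an eligibility flag for post-index enrolment. This much follows from the text alone.

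Removal of flagged patients is plausible but not instructed. If it occurred, it would condition eligibility on a post-index event and could bias treatment sequencing, DOT, PFS and OS.

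The number affected cannot be derived. It is tempting to multiply the 20–30% with a next therapy by a guessed trial share, but no such share is given. The 20–30% belongs to the 293-patient feasibility count and not to the 521 of Phase 3. Nor would those removed necessarily come from the group with a recorded next therapy, since Section 9.10.1 says that care outside the Network is not captured. The point rests on the wording and not on a count.

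**What to change.** In Table 1, set the period of the clinical trial participation row to available prior medical history up to the day before index date-1, and define the flag as enrolment in an interventional trial before index date-1 (alectinib or lorlatinib start, as applicable). Use the same wording, including the treatment of observational studies, in exclusion 2 of Sections 9.3.1 and 9.3.2. Add one sentence saying that enrolment after index date-1 does not affect eligibility and is only described. A separate category for trial therapy among the next treatments would be a convenient place for that description, but is optional.

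The cost is the wording of one table row and two criteria, plus a check that enrolment dates are available before index. There are two small drawbacks. Pre-index trial history may be incomplete, because Section 9.10.1 says that treatment before the first Network visit is not well captured. And the regimen of some patients who join a trial after index may be unknown.
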